2.0 Introduction

Transgender people commonly experience gender dysphoria defined as distress due to discord between their gender identity and birth sex.¹ The number of transgender Veterans (trans Vets) with gender dysphoria increased ~7-fold from 1,406 in 2006 to 9,608 in 2018 in VA.² Compared to non-trans Vets, trans Vets with gender dysphoria have > 2-fold hazard of suicide mortality.³ Gender-affirming treatments (GATs; e.g. surgery, hormones)⁴ are evidence-based treatments to reduce gender dysphoria, improve mental health and quality of life in trans people.⁵⁻⁹ Receipt of hormones and/or surgery reduced suicidal ideation by 62% among trans people¹⁰ with similar findings noted among trans Vets.¹¹ GATs are medically necessary for gender dysphoria.^{4,12-14} However, not much is known about the barriers and facilitators to accessing and receiving GATs in VA and VA Community Care (i.e., care paid for by the VA in the community)¹⁵ among trans Vets who desire GATs.

Barriers to receipt of GATs reported in a single-site VA study included delays in GAT receipt, need to travel for GATs, lack of clinician competency on trans health, discrimination, violence and lack of patient knowledge about VA GAT coverage.¹⁶ Additional barriers suggested by non-VA studies, include low income, housing instability, and cost of GATs.¹⁷⁻²¹ Barriers to GATs thus, reflect social determinants of health (SDOH) barriers (e.g. discrimination)²² and other barriers (e.g. lack of patient knowledge about GAT coverage). In our ongoing IIR 17-238 using VA data, trans Vets with SDOH barriers, including housing instability, financial strain, and violence were 38% less likely to receive hormones than those without SDOH barriers.²³ Trans Vets frequently experience SDOH barriers, with 28% experiencing housing instability, 31% unemployment, and 19.5% violence.²⁴ Thus, targeting SDOH barriers that are especially salient in the lives of trans Vets along with other barriers are promising approaches to improving GAT access and receipt in VA and VA Community Care (CC).

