We anticipate inviting approximately 10,000 trans Vets with a gender dysphoria diagnosis and/or self-reported gender identity as transgender and gender diverse to participate in the national survey and expect up to 1,500 will enroll and complete the survey. Recruitment for the national survey will consist of direct outreach to prospective research participants identified in Aim 1 through a mailed or emailed recruitment letter and Information Statement alerting Veterans about the survey, providing details about the individuals' rights as a research participant and inviting them to participate in the study. The letter will explain that the survey is entirely voluntary and that if they choose not to participate or to end the survey prior to completion, there will be no penalties or loss of VA benefits. The communication will make clear that the survey responses are confidential and that the Veteran's name or any other personally identifying information will not be used in any report of the survey results. The IRB's telephone number will be provided as a means for the potential participant to use to verify that the study constitutes VA research. Additionally, the study project manager's telephone number will be provided for the Veteran to call with questions about the study or if they wish to opt out of the study.

Veterans will be contacted as follows:

Contact	Method	Specifics
---------	--------	-----------

Contact 1	First Letter	All Veterans with a gender dysphoria diagnosis in the past 2 years and/or self-identified gender identity as transgender and gender diverse will be sent a recruitment letter via mail and/or email inviting them to participate in the study and offering the ability to opt-out, complete the survey online (either through mobile device, tablet or desktop), call in to the study project manager's number to complete the survey with the study manager or request that a paper survey is mailed to them.
Contact 2	Second letter	A second letter will be sent via mail and/or email approximately 10 days after the first letter.
Contact 3	Reminder Postcard	Approximately ten to twelve days after the second letter, we will send a reminder postcard and/or letter and/or email reinforcing basic information provided earlier and directing people to the website or to call the study project manager's number to complete the survey.

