5.6 Data Analysis

Database aim 1: The data analyst under the supervision of the PI will produce summary statistics (e.g., proportions, means) for gender-affirming receipt in VA and/or CC (VA/CC). We will characterize gender-affirming receipt by: 1) patient characteristics, including demographics (e.g. race), comorbidities (e.g. mental health conditions) commonly reported by trans individuals, utilization of VA care (e.g. primary care), 2) site (e.g. region, rural/urban) and 3) setting (VA/CC). As appropriate, two-sided chi-square test (categorical variables), t-test (continuous variables) or their nonparametric equivalent tests will be used to test for the statistical significance of the associations of these patient and site characteristics with gender-affirming receipt. We will also compare the characteristics of patients receiving gender-affirming treatment through VA vs. CC.

Survey aim 2: Our analytical goal is to identify barriers and facilitators associated with receipt of desired gender-affirming treatments in VA and/or CC. In keeping with this goal, the data analyst under the supervision of the PI, will conduct the following analyses:

Descriptive analyses: We will obtain summary statistics (e.g., proportions, 95% confidence intervals, etc.) of the distribution of each gender-affirming treatment, degree of receipt of desired gender-affirming treatments, barriers, and facilitators of gender-affirming treatment. We will characterize the degree of receipt of desired gender-affirming treatments in VA and/or CC. We will also characterize barriers and facilitators by degree of receipt of desired gender-affirming treatments in VA and/or CC, recognizing that trans Vets who received all desired gender-affirming treatments could encounter barriers in receipt of these gender-affirming treatments and trans Vets who received no desired gender-affirming treatments could encounter facilitators in trying to receive gender-affirming treatments. We will also characterize the degree of receipt of desired gender-affirming treatments, barriers and facilitators by age, race/ethnicity, gender identity (transfeminine, transmasculine, non-binary), and region.

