Primary analyses: We will conduct bivariate analysis to assess the unadjusted relation of barriers and facilitators with the dependent variables, receipt and desire of gender-affirming treatments in VA and CC. As appropriate, two-sided chi-square tests (categorical variables) or their equivalent non-parametric tests will be used to test the significance of any group differences. We will obtain odds ratios (ORs) and 95% confidence intervals (CI) from separate multivariable logistic regression models, to assess associations between barriers and facilitators for the dependent variables. A multinomial logistic regression model will be used to evaluate associations of barriers and facilitators with the ordinal dependent variable: degree of receipt of desired gender-affirming treatments. These models will adjust for covariates, such as age, race/ethnicity and gender identity. Further, depending on the distribution of respondents across sites, we will examine the distributions of the independent and dependent variables as well as the respondents' characteristics across sites. If there is substantial variation across sites and there are adequate number of respondents (at least 5) in each site, we will adjust for clustering of respondents within sites in the analyses. We will combine sites with small sample sizes into a single cluster for the analyses.

Secondary analyses: To assess interrelationships between barriers, we will examine the overlap of barriers by ascertaining the proportion of trans Vets with various combinations of barriers. To examine this overlap, we will create two variables: 1) a categorical variable, indicating combinations of different barriers (e.g., housing instability only, housing instability and employment, housing instability, unemployment and need to travel for gender-affirming treatments, etc.); 2) number of barriers. We will also explore the effects of these variables in models described in the primary analyses.

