Missing data: In a cross-sectional survey, we expect non-response to the entire survey (unit non-response) or to certain questions in the survey (item non-response). We will try to reduce unit non-response by sending two automated email reminders to Veterans to complete the survey. If we have $\geq 10\%$ unit non-response, we will examine the distribution of characteristics between respondents and non-respondents on measures (e.g., age, race/ethnicity, comorbidities, etc.) available in VA data. If necessary, we will create a weight as the inverse of the probability of response from a logistic regression model that predicts response and include these measures as independent variables. These weights will be used in all analyses to reduce bias due to unit non-response. To mitigate item non-response, we will use validated measures, improve the clarity of questions, and use survey branching logic to reduce response burden. Our primary analysis will assume that data are missing completely at random (MCAR) and include only subjects with complete information or computable variables. For items that have $\geq 10\%$ of missing data, we will examine patterns and predictors of missingness and conduct a sensitivity analysis by

imputing the values under the assumptions of missing at random conditional on the observed data. Comparing results from these analyses to that under the MCAR assumption will allow us to assess the amount of bias due to missing data. We will then adjust final models by including predictors of missingness accordingly.

All analyses will be conducted in SAS (SAS, Cary, NC) on complete data. Our tests of significance will be adjusted for multiple testing using the Benjamini-Hochberg procedure to control for the False Discovery Rate.

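### The Aim 2 secondary analysis sets out to assess how barriers are interrelated but reports only raw overlap, with no comparison to the overlap expected by chance

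*Combined protocol and SAP*

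**What the plan says.** All of this is in section 5.6 (Data Analysis, Survey aim 2) unless stated otherwise.

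- **Purpose and method.** The Secondary analyses paragraph reads: "To assess interrelationships between barriers, we will examine the overlap of barriers by ascertaining the proportion of trans Vets with various combinations of barriers". Two derived variables serve this: "a categorical variable, indicating combinations of different barriers", and the number of barriers.
- **Further use.** "We will also explore the effects of these variables in models described in the primary analyses".
- **What those models relate.** The Primary analyses begin with "bivariate analysis to assess the unadjusted relation of barriers and facilitators with the dependent variables, receipt and desire of gender-affirming treatments in VA and CC". The logistic and multinomial models that follow also have receipt, desire or degree of receipt as the dependent variable.
- **Single-barrier summaries.** The Descriptive analyses begin "We will obtain summary statistics (e.g., proportions, 95% confidence intervals, etc.) of the distribution of each gender-affirming treatment", and the same sentence extends to barriers and facilitators. Nothing says these single-barrier proportions will be set against the combination proportions.
- **Multiplicity.** "Our tests of significance will be adjusted for multiple testing using the Benjamini-Hochberg procedure to control for the False Discovery Rate". No test of one barrier against another is named.
- **Planning figures.** Section 2.0 (Introduction) describes trans Vets "with 28% experiencing housing instability, 31% unemployment, and 19.5% violence". Section 5.2 (Recruitment Methods) gives the survey size: "expect up to 1,500 will enroll and complete the survey".

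**The concern.** The stated question is whether barriers are related to each other. The stated statistic is how many Veterans have each combination. These are different quantities. A joint proportion shows how often barriers occur together. Whether that is more or less often than unrelated barriers would occur together depends on their separate prevalences, and the plan makes no such comparison.

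The model step does not supply it, because those models relate barriers to treatment receipt or desire, not to each other.

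What is at stake is the reading of one secondary table. Common barriers may look like a cluster only because they are common, and less common barriers that truly occur together may be overlooked. The survey findings are to be integrated with the interviews when patient-centered strategies are developed (section 5.6, Qualitative aim 3), so a mistaken statement about which barriers go together could carry forward.

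**Working it through.** The plan gives no expected-overlap or power figure for this analysis, so there is nothing of its own to reproduce.

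**Inputs.** From the Introduction, used as planning values: housing instability 0.28, unemployment 0.31, violence 0.195. From Recruitment Methods: N up to 1,500. Assumed: barriers at 10%, 15% or 20%, the odds ratios (OR), lower values of N, and a two-sided alpha of 0.05.

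**Step 1. Overlap if barriers are unrelated.** Expected joint proportion = p1 × p2.

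| Pair | Expected overlap | Of 1,500 |
|---|---|---|
| Housing, unemployment | 0.28 × 0.31 = 8.7% | 130 |
| Unemployment, violence | 0.31 × 0.195 = 6.0% | 91 |
| Housing, violence | 0.28 × 0.195 = 5.5% | 82 |

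All three: 0.28 × 0.31 × 0.195 = 1.7%. Exactly two: 0.0699 + 0.0377 + 0.0435 = 15.1%. Two or more is therefore 16.8%, about 252 of 1,500, with no relation between any of the barriers.

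**Step 2. Dependence on prevalence.** For two unrelated barriers of equal prevalence, overlap is 1% at 10% prevalence, 4% at 20%, 9% at 30% and 25% at 50%.

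**Step 3. Can the ranking reverse?** For a given OR, the joint proportion x solves OR = x(1 − p1 − p2 + x) / [(p1 − x)(p2 − x)]. With p1 = p2 = 0.10 and OR = 5, x = 0.0297. Check: 0.0297 × 0.8297 / 0.0703² = 5.0. So the strongly linked pair overlaps in 3.0%, about three times its chance value of 1%, yet well below the 8.7% of the unlinked 28%/31% pair.

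Conversely, an overlap of 8.68% corresponds to OR 1.0 at prevalences of 28% and 31%. It corresponds to 0.0868 × 0.6868 / 0.1132² = 4.7 if both prevalences are 20%, and 0.0868 × 0.7868 / 0.0632² = 17 if both are 15%.

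**Step 4. Does a benchmark resolve this?** For housing instability and unemployment, against 8.7% expected:

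| True OR | Observed overlap | Observed/expected |
|---|---|---|
| 1.5 | 10.5% | 1.21 |
| 2 | 11.8% | 1.36 |
| 3 | 13.7% | 1.57 |
| 5 | 15.9% | 1.84 |

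**Step 5. Is it estimable at the planned size?** Power of a 1-df chi-square test of independence uses noncentrality N × φ², with φ = (x − p1p2) / √[p1(1 − p1)p2(1 − p2)]. For OR 1.5, φ = 0.0866, so at N = 1,500 the noncentrality is 11.2 and power is 92% before any multiplicity adjustment. At N = 500 it is 49%. For OR 2, power is over 99% at N = 1,500 and 92% at N = 500.

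**Step 6. Cost of the adjustment.** With 10 barriers (assumed) there are 10 × 9 / 2 = 45 pairs. If only one is linked, the Benjamini-Hochberg threshold for it is about 0.05 / 45 = 0.0011, a critical value of 3.26. Power for OR 1.5 at N = 1,500 is about Φ(√11.24 − 3.26) = Φ(0.09), or 53% to 54%. At N = 600 it is about 13%. This is the worst case; the threshold is less strict when more pairs are linked.

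**The case against.** The strongest reply is that this is a descriptive secondary analysis. The share of Veterans facing several barriers at once is useful for planning services whether or not the barriers are statistically related, and the plan's sentence itself goes on to speak of overlap. That stands: the proportions are valid as a description of co-occurrence. The gap concerns only the stated purpose.

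Two stronger readings are tempting and are not supported.

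- **A reader might infer that the study cannot tell linked barriers from unlinked ones.** That is true of the analysis as written, not of the data. The single-barrier proportions are already planned, and a combination variable that covers all combinations amounts to the full cross-classification. Expected overlap follows directly from these; the plan just does not commit to deriving it.
- **A reader might infer that the count of barriers will credit barriers that have no association with receipt.** This presumes a linear, per-barrier interpretation that the plan does not state. It also overlooks the companion combination variable, which has single-barrier categories (housing instability alone is one of the examples) and enters the same models. If only one barrier mattered, that variable could show it. A significant count in that situation would be a correct detection of a real association between the count and receipt, not a false positive.

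It is also fair to say that no passage ties the overlap table to a particular choice of strategy, so the downstream consequence is possible rather than documented.

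**Conclusion.** The point holds as a mismatch between stated purpose and stated statistic in one secondary analysis. No association between barriers is specified anywhere in the plan, and raw overlap follows prevalence closely enough to reverse the order of true associations: 8.7% for an unlinked pair against 3.0% for a pair linked at OR 5.

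The size rests on background prevalences rather than survey results, on an assumed 10% prevalence and OR for the linked pair, and on 1,500 as an upper limit for N. At the Introduction's prevalences chance overlap is about 5% to 9% per pair; for barriers near 10% it is about 1%, and the risk of over-reading any single overlap is correspondingly smaller.

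The primary analyses of barriers against receipt and desire are unaffected. This is a worthwhile, inexpensive improvement, not a flaw in the main design.

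**What to change.** In section 5.6, Survey aim 2, Secondary analyses:

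1. Keep the combination proportions and describe them as co-occurrence.
2. For each pair of barriers, also report observed and expected overlap (expected = product of the two prevalences among the same respondents), or the pairwise odds ratio, with a 95% CI.
3. State that any conclusion about interrelationships rests on these measures and not on the size of the overlap.
4. If pairwise tests are done, include them in the planned Benjamini-Hochberg adjustment.

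If the team wants only a description, the minimum alternative is to reword the purpose as describing co-occurrence and to draw no conclusion about relations between barriers.

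The cost is a few lines of SAP text and one or two tables from data already being collected. The downside is a larger test family: power for a pairwise OR of 1.5 would fall below the unadjusted 92% at N = 1,500, to a little over half in the worst case worked above. Reporting estimates with confidence intervals and without tests avoids enlarging the family.

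### The missing-data trigger is set per item, so a multivariable model can lose 10% or more of respondents unexamined; when it does fire, the bias comparison overclaims and the final-model adjustment has no limits

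*Combined protocol and SAP*

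**What the plan says.** All of this is in section 5.6 of the combined protocol and SAP, mainly under Missing data for survey Aim 2.

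- Primary handling of item non-response: "Our primary analysis will assume that data are missing completely at random (MCAR) and include only subjects with complete information or computable variables".
- For items at least 10% missing, and only for those, the plan calls for missingness diagnostics and a sensitivity analysis. The method is "imputing the values under the assumptions of missing at random conditional on the observed data".
- Use of the result: "Comparing results from these analyses to that under the MCAR assumption will allow us to assess the amount of bias due to missing data". Then: "We will then adjust final models by including predictors of missingness accordingly".
- Closing statement: "All analyses will be conducted in SAS (SAS, Cary, NC) on complete data".

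Unit non-response has its own 10% trigger and its own remedy, response weights: "These weights will be used in all analyses to reduce bias due to unit non-response". That rule does not cover skipped questions. Under Primary analyses, the models are multivariable logistic and multinomial regressions of receipt and desire on barriers and facilitators. The named covariates are age, race/ethnicity and gender identity.

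**The concern.** The trigger watches the wrong quantity. A complete-case model keeps only people with every model variable present, so what matters is the share lost from the model, and no rule looks at that share. Precision would be lost, and any selectivity in who is dropped would go unexamined, although each item looked acceptable alone.

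The two follow-on rules matter only when an item does reach 10%. If agreement between complete-case and MAR results is read as the size of the bias, agreement can be reported as no bias. If any variable found to predict missingness can enter the outcome model, the reported odds ratio (OR) may answer a different question from the one intended. Section 5.5 lists candidates such as depression, minority stress and quality of life, and does not say where they stand relative to barriers and receipt.

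The complete-data statement also conflicts with the imputation planned a few sentences before it.

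**Working it through.** The plan gives no expected item missingness, model size or complete-case sample size, so there is no figure of its own to reproduce. All rates below are assumptions.

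**1. Respondents lost from a model**

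The base case has k = 3 survey variables: outcome, one barrier and gender identity. Age and race/ethnicity are assumed to come from VA records, because section 5.6 lists them among characteristics compared "on measures (e.g., age, race/ethnicity, comorbidities, etc.) available in VA data". The plan does not say they will be filled from there; if they are not, k = 5. Each variable is missing a share p.

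- Independent skips: loss = 1 − (1 − p)^k.
- Skips clustered within persons: propensity Beta(5p, 5(1 − p)), intraclass correlation 1/6 (assumed).
- Full overlap: loss = p.
- Standard error (SE) inflation = 1/√(1 − loss) − 1.

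| p | k | Independent | Clustered | Full overlap |
|---|---|---|---|---|
| 2% | 3 | 5.9% (SE +3.1%) | 5.0% (SE +2.6%) | 2% (SE +1.0%) |
| 5% | 3 | 14.3% (SE +8.0%) | 12.2% (SE +6.7%) | 5% (SE +2.6%) |
| 2% | 5 | 9.6% | 7.2% | 2% |
| 5% | 5 | 22.6% | 17.3% | 5% |

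For p = 5%, k = 3: 1 − 0.95³ = 0.143, and 1 − (4.75/5)(5.75/6)(6.75/7) = 0.122. Model loss reaches 10% once items average 3.5% (independent) to 4.1% (clustered) missing with three variables, or 2.1% to 2.8% with five. The per-item trigger fires in none of these cases.

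**2. Does the comparison show the amount of bias?**

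Assume 28% have the barrier (the housing-instability figure in section 2.0), logit P(receipt) = 0.2 + ln(0.5) × barrier, and only the barrier item missing. Let m10 and m11 be its missing rates among people with the barrier, without and with receipt. The rate without the barrier is 6%. Then complete-case OR = 0.50 × (1 − m11)/(1 − m10).

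| m10, m11 | Item missing | Complete-case OR | OR imputed from outcome | True OR |
|---|---|---|---|---|
| 22%, 22% | 10.5% | 0.50 | 0.50 | 0.50 |
| 25%, 15% | 10.3% | 0.57 | 0.57 | 0.50 |
| 30%, 10% | 10.6% | 0.64 | 0.64 | 0.50 |
| 40%, 10% | 12.3% | 0.75 | 0.75 | 0.50 |

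The comparison reads zero in every row. Adding a linked record indicator to the imputation in the last row (assumed sensitivity 60%, specificity 95%) gives 0.638. The comparison then shows ln(0.750/0.638)/ln(0.750/0.500) = 0.40 of the bias on the log scale.

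**3. Adding a predictor of missingness to the outcome model**

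Take no missing data, 28% with the barrier, and logit P(receipt) = 0.4 + ln(0.6) × barrier + ln(0.5) × predictor.

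- Predictor present in 60% with and 30% without the barrier: P(receipt) is 0.374 and 0.547, so the OR without the predictor is (0.374/0.626)/(0.547/0.453) = 0.495. With it, the OR is 0.60.
- Predictor present in 40% of both groups: the OR moves only from 0.61 to 0.60.

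In the first case, 0.60 is the better answer if the predictor is a confounder. If it lies between barrier and receipt, 0.60 leaves out part of the total effect.

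A second example includes missing data. The barrier raises an intermediate predictor from 20% to 50%; its OR for receipt is 0.40, the barrier's direct OR is 0.75, and data are missing in 30% with and 5% without the predictor. The total OR is 0.581 and complete-case gives 0.598. Adding the predictor gives 0.75, further from the total effect.

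**The case against.** The strongest reply is that the loss may never arise. Section 5.2 pays the gift card only to those who answer every question, which should reduce scattered skips. Sections 5.2 and 5.7 keep partial surveys and allow people to stop part-way, so the same people would tend to miss many items. That pushes towards full overlap, where the per-item trigger works much like a model-level one. At 2% missing, the three-variable loss stays under 10% anyway, and the plan's allowance for computable variables may rescue some scales. All of this stands: it makes the loss uncertain, but it does not supply the missing rule.

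On the comparison, the plan already calls the imputation a sensitivity analysis and conditions it on observed data, to which section 5.1 links VA records. The exact zero in the table comes from imputing one variable from the outcome alone, and an auxiliary breaks it. That also stands, but the auxiliary recovered only part of the bias, and the wording still claims to show its amount.

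On the adjustment rule, a reader might infer that it is simply wrong. The documents do not support that. Conditioning on a confounder, or on a covariate that alone drives missingness and is not on the pathway, is legitimate, and a predictor unrelated to the barrier changes little. The fault is that nothing separates these cases from a predictor on the pathway.

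A reader might also count every barrier named in section 2.0 as a required survey item and infer far larger losses for the number-of-barriers variable. Section 2.0 is background, not the questionnaire, and that analysis is secondary and exploratory.

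**Conclusion.** The point holds, with limits. The trigger is per item, the models are multivariable and complete-case, and no rule covers the share lost from a model. With three survey variables at 5% missing the loss is 12% to 14%, falling to 5% under full overlap. These sizes rest on assumed item rates, an assumed model size and an assumed degree of clustering. They show what the rule permits and do not forecast the survey. A reader might infer that the complete-case ORs are biased; the documents do not show that, and the demonstrated cost is modest precision loss that nobody is required to examine.

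The two follow-on rules apply only once an item reaches 10%. The bias comparison overclaims: in the worked case both analyses give 0.75 against a true 0.50. The adjustment rule is unrestricted: it can move an OR from 0.495 to 0.60, which may be right or wrong depending on the role of the added variable. Both should be corrected before results are seen.

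**What to change.** 1. Report the number excluded from each model. For any primary model in which 10% or more of eligible respondents are excluded for item non-response, report multiple imputation beside the complete-case result. Eligible means those to whom the model applies (for receipt of desired treatment, Veterans who desire it); planned branching skips do not count. Complete-case can remain primary.
2. Replace the amount-of-bias wording with: sensitivity of results to the MCAR versus MAR assumption.
3. Put predictors of missingness, including linked VA record variables, in the imputation model with the outcome, barriers, facilitators and covariates. Add them to the outcome model only if prespecified as confounders, or as a labelled sensitivity analysis.
4. Limit the complete-data statement to the complete-case analysis.

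The cost is a few SAP sentences, standard SAS procedures and modest extra analysis and reporting; the record linkage is already planned. The 10% level is a judgement that reuses the plan's own threshold. The primary estimate keeps its precision loss, and MAR imputation does not remove bias from missingness that depends on unseen values, though linked records may reduce it.
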